6.1.5 CO DOSING ALGORITHM USING THE CFK EQUATION

For subjects randomized to iCO, iCO (200 ppm) will be administered for up to 20 minutes as a "test dose" on each day to determine the subject's CFK equation-determined dose. The COHb level will be measured prior to the test dose and 20 minutes after the test dose. These two COHb levels will be used in the CFK equation to determine each subject's specified dose in order to achieve a COHb level of 6-8%. After the CO dose is determined, subjects will be administered inhaled CO at the algorithm-determined dose- not to exceed 500 ppm or 90 minutes total (including test dose). Subjects randomized to placebo will be administered medical grade air.

1. Arterial or venous blood will be drawn for baseline blood gas analysis and COHb measurements prior to iCO or placebo administration.
2. Subjects randomized to CO will be treated with inhaled CO at 200 ppm for 20 minutes (test dose).
3. After 20 minutes, blood will be drawn for COHb measurement.
4. DLCO will be estimated using the baseline and 20 min COHb in the CFK equation calculator program, and used to compute the iCO dose to achieve a COHb level of 7% (target 6-8%) at 90 minutes.
5. Dose will be adjusted (200-500 ppm) in subjects randomized to CO based on CFK equation-determined dose.
6. Blood will be drawn for COHb measurements at 20 min, 40 min, 60 min, 75 min, 90 min, and 3 hours. Blood will also be drawn for blood gas analysis at 90 min.

On days 1-3, a total of approximately 3 mL of blood will be drawn during the study drug administration for safety monitoring of COHb levels and blood gas analysis.

6.1.6 DAILY HOLD PARAMETERS PRIOR TO STUDY DRUG ADMINISTRATION

Subjects will be assessed daily prior to study drug administration as described in the **Schedule of Activities (Section 1.3)**.

Administration of the study drug will be held if the following criteria are met.

- COHb level $\geq 3\%$
- Lactate ≥ 4 mmol/L
- ST elevation MI or unstable angina/non ST elevation MI concerning for ACS
- Unstable atrial or ventricular arrhythmia

Subjects will have blood drawn daily for measurement of COHb and lactate prior to administration of study drug. If COHb $\geq 3\%$ or lactate ≥ 4 mmol/L, the study drug will be held until the next scheduled dose the following day. Lactate and COHb will be measured the following day to determine whether the study drug will be administered. If the study drug is being held for another reason, COHb levels will not be measured on days the study drug is being held.

A 12 lead EKG will also be performed and reviewed daily by the study staff physician prior to study drug administration to evaluate for cardiac exclusion criteria (eg. acute MI, acute coronary syndrome (ACS), or unstable atrial or ventricular arrhythmia). If a subject meets the following criteria for ST elevation MI or unstable angina/non ST elevation MI concerning for ACS according to the American College of Cardiology Foundation/American Heart Association guidelines¹⁴⁰⁻¹⁴², they will be excluded from enrollment or further study drug administration according to exclusion criteria.

ST elevation MI (STEMI) Criteria: New ST elevation at the J point in at least 2 contiguous leads of ≥ 2 mm (0.2 mV) in men or ≥ 1.5 mm (0.15 mV) in women in leads V2–V3 and/or of ≥ 1 mm (0.1 mV) in other contiguous chest leads or the limb leads; New or presumably new left bundle branch block (LBBB)¹⁴⁰⁻¹⁴².

Unstable angina/non ST elevation MI (NSTEMI): Ischemic ST-segment depression ≥ 0.5 mm (0.05 mV) or dynamic T-wave inversion with pain or discomfort; Nonpersistent or transient ST-segment elevation ≥ 0.5 mm for < 20 minutes. Threshold values for ST-segment depression consistent with ischemia are J-point depression 0.05 mV (-0.5 mm) in leads V2 and V3 and -0.1 mV (-1 mm) in all other leads (men and women)¹⁴⁰⁻¹⁴².

Note, troponin (I or T) may be increased in patients with sepsis and ARDS¹⁴³ in the absence of an acute MI or ACS from coronary artery disease. If, in the judgment of the clinical team, an ARDS patient with elevated troponin levels has no other indication of an MI or ACS, the patient may still be eligible for enrollment.

In addition, if a subject develops the following criteria during the study, the study drug will be held until resolved:

- Severe hypoxemia defined as $\text{SpO}_2 < 95$ or $\text{PaO}_2 < 90$ on $\text{FiO}_2 \geq 0.9$
- Hemoglobin < 7.0 g/dL
- Diffuse alveolar hemorrhage from vasculitis
- Use of high frequency ventilation
- Use of inhaled pulmonary vasodilator therapy (eg. NO or prostaglandins)
- Use of ECMO

If study drug hold criteria are met, the study drug will be held and subjects will be evaluated on a daily basis and assessed for whether a given criteria has resolved and whether study drug treatment may be resumed.

6.1.7 INTERRUPTION OF DOSING DURING STUDY DRUG ADMINISTRATION

Subjects will have blood drawn for measurement of COHb levels prior to study drug treatment and 20 min, 40 min, 60 min, 75 min, 90 min, and 180 min after the start of study drug treatment. It is anticipated that COHb levels will not exceed the target range of 6-8% given the impaired diffusion capacity in ARDS patients and CFK equation-determined personalized iCO dosing algorithm. However, the following parameters will be used to shorten the 90 minute treatment duration should CO uptake be higher than anticipated:

The study drug will be stopped prior to 90 minutes:

1. If the measured COHb level is > 8% at any time during study drug treatment.
2. If the investigator, attending physician, the patient, or their surrogate decides that the study drug should be discontinued.

If COHb levels unexpectedly exceed our target level, in addition to discontinuation of the study drug, subjects will be placed on 100% O₂ to accelerate CO elimination until COHb levels normalize.

6.1.8 PERMANENT DISCONTINUATION OF STUDY DRUG

Permanent discontinuation of the study drug is defined as cessation of the study drug without the intent of restarting the study drug during the three-day treatment period.

Permanent discontinuation of the study drug inhalation will occur in the following situations:

- **Occurrence of pre-specified administration-related AEs:**
 - Acute MI* within 48 hours of study drug administration
 - Acute stroke** within 48 hours of study drug administration
 - New onset atrial or ventricular arrhythmia requiring DC cardioversion within 48 hours of study drug administration
 - Increased oxygenation requirements defined as: an increase in FiO₂ of ≥ 0.2 AND increase in PEEP ≥ 5 cm H₂O within 6 hours of study drug administration.
 - Increase in any protocol-specified measurement of COHb ≥ 10%
 - Increase in lactate by ≥ 2 mmol/L within 6 hours of study drug administration
- If the subject experiences serious adverse events (SAEs) **related to the study drug**
- If the investigator, attending physician, the patient or their surrogate decides that the study drug should be discontinued. If this decision is made because of an AE, then appropriate AE reporting procedures will be followed (**Section 8.7**).
- Daily baseline COHb levels ≥ 3% leading to three missed drug doses
- Three or more missed drug doses due to AEs

* Acute MI is defined below according to the Executive Group on behalf of the Joint European Society of Cardiology (ESC)/American College of Cardiology (ACC)/American Heart Association (AHA)/World Heart Federation (WHF) Task Force for the Universal Definition of Myocardial Infarction¹⁴⁴. We will also rely upon subspecialty consultation to confirm the presence or absence of an acute MI.

Acute myocardial infarction is defined as acute myocardial injury with clinical evidence of acute myocardial ischemia and with detection of a rise and/or fall of cardiac troponin values with at least 1 value above the 99th percentile upper reference limit and at least 1 of the following:

- Symptoms of myocardial ischemia;
- New ischemic ECG changes;
- Development of pathological Q waves;
- Imaging evidence of new loss of viable myocardium or new regional wall motion abnormality in a pattern consistent with an ischemic etiology;
- Identification of a coronary thrombus by angiography or autopsy (not for types 2 or 3 MIs).

** Acute stroke is defined as an acute neurological deficit attributed to an acute focal injury of the central nervous system by a vascular cause, including cerebral infarction, intracerebral hemorrhage, and subarachnoid hemorrhage based on neuropathological, neuroimaging, and/or other clinical evidence of permanent injury¹⁴⁵. We will also rely upon subspecialty consultation to confirm the presence or absence of an acute stroke.

Subjects who have their study drug permanently discontinued will continue their participation in the study, and will be followed to determine their vital status and perform neurocognitive testing at 3 and 6 months, as outlined in the **Schedule of Activities (Section 1.3)**.

6.1.9 COMPLETION OF THE STUDY DRUG ADMINISTRATION

Subjects will be considered to have completed the study drug administration portion of the study when one of the following conditions is met, whichever comes first:

1. Three days after study drug administration
2. Discontinuation of mechanical ventilation
3. Death
4. Pre-specified criteria met for permanent discontinuation of study drug (**Section 6.1.8 in the Study Protocol**)

6.1.10 TREATMENT IN COVID-19 SUBJECTS

For enrolled pneumonia or ARDS patients with COVID-19 infection, all research and clinical staff will conform to each site's hospital infection control guidelines for COVID-19 positive patients with appropriate personal protective equipment (PPE) for enhanced respiratory isolation precautions. All research and clinical staff will have appropriate training on PPE, be fit-tested, and wear an N95 respirator or powered air-purifying respirator (PAPR) if staff cannot be fit-tested, face shield or other eye protection, gloves, and gown when entering the subject's room for treatment or sample collection. Gown, gloves, and eye protection will be doffed upon exiting the subject's room either just inside or just outside the door, and hand hygiene will be performed. Respiratory protection should be removed after exiting the subject's room unless extended use is being practiced.

During study drug treatment, all staff will conform to each site's hospital infection control guidelines regarding treatment of COVID-19 positive mechanically ventilated patients with inhaled therapies. Staff will be limited to essential personnel in the room. All equipment will be single-use or dedicated to use of

the subject to avoid sharing with other subjects. Reusable equipment will be disinfected with a hospital-approved disinfectant before use in another subject.

Blood sample collection and handling will be performed according to each site's hospital infection control guidelines for COVID-19. Samples obtained from a subject will be put in a tube by research or clinical staff, and the tube will be wiped down with a hospital-approved disinfectant. While holding the tube with the wipe, the specimen tube will be carefully placed into a clean specimen bag held by a monitor or nurse outside the room. The specimen bag will in turn be wiped down with a hospital-approved disinfectant. A member of the research team will pick up the research specimens and transport them to a BSL2+ laboratory in a secondary container. Research samples will only be processed in hospital biosafety committee approved BSL2+ laboratory facilities.

6.2 PREPARATION/HANDLING/STORAGE/ACCOUNTABILITY

6.2.1 ACQUISITION AND ACCOUNTABILITY

Each participating site is responsible for the ordering, storing and dispensing of the investigational agent(s). Each study team will be responsible for keeping a Site Drug Accountability Log at the site which will include a log of CO/placebo air tanks with lot number/cylinder number, concentration, expiration date, and dates received from/returned to Praxair. A subject study drug accountability log will record the subject ID, cylinder number, content of tank, dose (ppm), date dispensed, and tank pressure at start/end of treatment.

6.2.2 FORMULATION, APPEARANCE, PACKAGING, AND LABELING

The study drug will be provided for this study by Praxair Healthcare Services. Gas mixtures will be manufactured with United States Pharmacopeia (USP)/Ultra High Purity (UHP)/National Formulary (NF) components. The mixtures will be prepared as a Certified Standard with a blend tolerance of $\pm 10\%$ and analytical uncertainty of 2%.

The gas mixture provided to subjects randomized to CO will be 5000 ppm CO (balance air) and will be provided to study sites by Praxair Healthcare Services in AG or A3 aluminum cylinders with a CGA 500 valve. The gas cylinder's nominal size is 5 inches in diameter by 17 inches tall, contains 360 liters of 5000 ppm (0.5%) CO in room air (21% oxygen), and poses no increased flammability risk. The 5000 ppm CO source gas will be administered via the CO Delivery System (12th Man Technologies, Garden Grove, CA) and delivered to subjects at a CFK equation-determined individualized dose (200-500 ppm) to achieve a target COHb level of 6-8%.

The mixture components include: **Carbon Monoxide UHP Grade 3.0** (Assay 99.9%; O₂ < 10 ppm, H₂O < 5 ppm, N₂ < 900 ppm and CO₂ < 20 ppm); and **Medical Air USP**. The source materials for **Medical Air USP** include: **Oxygen USP** (Assay $\geq 99.2\%$; Odor- none; Oxygen produced by air liquefaction process, does not require CO and CO₂ analysis); and **Nitrogen NF USP** (Assay $\geq 99.2\%$; Identification- OK, Paramagnetic Assay Method; CO ≤ 10 ppm; Odor- none).

The gas mixture provided to subjects randomized to placebo will be medical grade air and will be provided to study sites by Praxair Healthcare Services in AG or A3 aluminum cylinders with a CGA 346 valve. With the exception of the 346 valve, the placebo gas cylinders will be identical in size and color as the CO cylinders. The placebo gas will be administered via the CO Delivery System (12th Man Technologies,

Garden Grove, CA) and delivered to subjects in an identical fashion as iCO delivery.

6.2.3 PRODUCT STORAGE AND STABILITY

The CO and placebo air cylinders will be stored at room temperature in a secure area at each center. The cylinders will be stored and handled according to each site's Compressed Gas Cylinder Storage Guidelines. The CO and placebo air cylinders will be returned to Praxair upon expiration. The expiration date is generally three years from the date of fill and is clearly indicated on the certificate of analysis for each cylinder.

6.2.4 PREPARATION

As described in the SOP, the CO Delivery System will be calibrated and performance testing conducted daily prior to use. The calibration will be performed as described in the Operator's Manual in **Appendix A**. The calibration consists of a low (21%) and high (100%) range O₂ calibration, followed by a low (100 ppm) and high (400 ppm) range CO calibration. After completion of the calibration, performance testing will be performed as described in the SOP. The CO Delivery System will be assembled, the appropriate gas cylinder (CO or air) connected, and the delivery system will be connected to the ventilator as described in **Appendix A**. As shown in **Figure 9**, the injector module will be connected between the inspiration port of the ventilator and inlet port of the humidifier. The gas sampling line will be placed between the outlet port of the humidifier and the patient wye as shown.

6.3 MEASURES TO MINIMIZE BIAS: RANDOMIZATION AND BLINDING

Eligible participants will be randomized to one of the two treatment arms using a permuted block method¹⁴⁶ with random block sizes. The randomization ratio will be 2:1 iCO:placebo. The randomization will not be stratified by any factors. The study biostatistician will verify all the necessary randomization information (blinding method, randomization method, block size, and number of treatment groups) in the StudyTRAX randomization configuration module.

Site investigators will review all potential study participants with one of the CCC physician members. Following informed consent, the unblinded administering RT or physician or blinded study coordinator will randomize subjects in the database using the StudyTRAX randomization tool. The unblinded administering RT or physician will obtain the subject's treatment assignment through the "View Treatment" button in the blinded database, a privilege granted to unblinded RTs and physicians only. CO-related measurements (SpCO, COHb, ambient CO) and drug-related information will be in a separate project within the database, which the blinded study coordinators will not have access to. Permission to this limited-access project will only be granted to unblinded study personnel by the PI, as it contains treatment-specific information such as CO monitoring and study drug administration data.

The study drug assignment will be blinded to the subject, clinical team, study coordinators, and other study staff with the exception of the administering study staff (RT and physician OR physician alone), who will be unblinded to the treatment assignment to ensure subject safety. We chose this partially double-blind design to ensure safe iCO administration and an unblinded assessment of COHb levels in order not to exceed potentially toxic thresholds.

To maintain blinding, the placebo air cylinders are identical in appearance as the CO cylinders (with the exception of different CGA valves required by the manufacturer Praxair). Cylinders will also be shrouded in dark sleeves to ensure blinding. The placebo air will be administered via inhalation via the COventDS

and delivered to subjects in an identical fashion as those randomized to CO. To ensure that the subject, study coordinator, and clinical staff remain blinded to the study drug assignment, the administering RT and physician study staff member OR physician study staff member alone will conceal the gas cylinders, CO delivery device, and measurements of COHb, SpCO, and ambient CO levels. Unblinded test results will be kept in a separate location from the blinded test results and concealed from the study coordinators.

The unblinded administering physician will be responsible for maintaining a separate password-protected limited-access project within the database with the subject identification number and CO-related measurements (SpCO, COHb, ambient CO) which the study coordinator will not have access to. While the administering investigator will be unblinded throughout the study due to safety monitoring, they will only be unblinded to the treatment assignment for subjects enrolled at their own site. Investigators will otherwise be blinded to the study treatment assignment for subjects enrolled at the other sites. The lead RT ([name]) may become unblinded to the treatment assignments at other sites to assist with study drug administration procedures if necessary.

If the clinical team believes that unblinding is medically necessary in order to properly treat the patient, the unblinded administering physician can disclose study product assignment. If there is time to do so, the unblinded administering physician should discuss this unblinding with the unblinded CCC physician prior to the disclosure. All episodes of unblinding, whether deliberate or inadvertent, will be reported to the DSMB at the next routine report.

A blinded study physician at each site will review all AEs and will assess their relationship to the study intervention. Additional AE adjudication will be provided by one of the Medical Monitors ([name] or [name]). In addition to blinded adjudication of AEs, investigators blinded to treatment allocation will assess chest X-rays required for the calculation of the LIS score. De-identified chest X rays at each site will be reviewed centrally by blinded investigators at BWH.

6.4 STUDY INTERVENTION COMPLIANCE

To assess protocol adherence during monitoring visits, the CCC will review the Study Drug Administration and CO Administration Monitoring forms, in addition to the Study Drug Accountability Logs. The administering RT and physician study staff member OR physician study staff member alone will keep track of study drug assignment and dosages, time and duration of treatment, tank lot number, and COHb results on Subject Drug Administration and CO Administration Monitoring forms. These forms should be kept in a secure place and confidential from blinded study staff.

Each participating site is responsible for the ordering, storing and dispensing of the investigational agent(s). Each study team will be responsible for keeping a Site Drug Accountability Log at the site which will include a log of CO/placebo air tanks with lot number/cylinder number, concentration, expiration date, and dates received from/returned to Praxair. A subject study drug accountability log will record the subject ID, cylinder number, content of tank, dose (ppm), date dispensed, and tank pressure at start/end of treatment.

6.5 CONCOMITANT THERAPY

Subjects will be excluded from participation in the study if they are receiving concomitant inhaled pulmonary vasodilators continuously (such as inhaled nitric oxide [NO] or prostacyclin), as these inhaled medications may interfere with the dosing of inhaled CO. If a decision is made by the clinical team to

initiate these medications in enrolled subjects following randomization and within the 3-day study treatment period, the study drug will be held until subjects are no longer receiving these medications concomitantly. The study drug may be reinitiated following cessation of these inhaled medications if there are no other protocol-specified reasons that preclude ongoing treatment in the study. Potential subjects will also be excluded if they are participating in another investigational drug study. There are otherwise no contraindications to concomitant medications in the study.

7 STUDY INTERVENTION DISCONTINUATION AND PARTICIPANT DISCONTINUATION/WITHDRAWAL

7.1 DISCONTINUATION OF STUDY INTERVENTION

Discontinuation from study drug does not mean discontinuation from the study, and remaining study procedures should be completed as indicated in the study protocol. If a clinically significant finding is identified (including, but not limited to changes from baseline) after enrollment, the site investigator or designee will determine if any change in participant management is needed. Any new clinically relevant finding will be reported as an AE.

Permanent discontinuation of the study drug is defined as cessation of the study drug without the intent of restarting the study drug during the three-day treatment period. Subjects who have their study drug permanently discontinued will continue their participation in the study, and will be followed to determine their vital status and perform neurocognitive testing at 3 and 6 months as outlined in the **Schedule of Activities (Section 1.3)**.

Criteria for permanent discontinuation of the study drug are described in **Section 6.1.8**. In some instances, the study drug may be held and the subject may be re-evaluated for treatment on subsequent days. The criteria for a study drug hold are described in **Section 6.1.6**.

If study drug hold criteria are met, the study drug will be held and subjects will be evaluated on a daily basis and assessed for whether a given criteria has resolved and whether study drug treatment may be resumed.

7.2 PARTICIPANT DISCONTINUATION/WITHDRAWAL FROM THE STUDY

Participants are free to withdraw from participation in the study at any time upon request. An investigator may discontinue or withdraw a participant from the study for the following reasons:

- If any clinical AE, laboratory abnormality, or other medical condition or situation occurs such that continued participation in the study would not be in the best interest of the participant
- Disease progression which requires discontinuation of the study intervention
- If the participant meets an exclusion criterion (either newly developed or not previously recognized) that precludes further study participation
- Participant unable to receive at least one dose of the study drug

If a patient or surrogate requests withdrawal from the study, the investigators will seek explicit permission to continue data collection.

The reason for participant discontinuation or withdrawal from the study will be recorded on the Case Report Form (CRF). Subjects who sign the informed consent form and are randomized but do not receive the study intervention may be replaced. Subjects who sign the informed consent form, and are randomized and receive at least one dose of the study product, and subsequently withdraw, or are withdrawn or discontinued from the study will not be replaced.

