5.2 EXCLUSION CRITERIA

An individual who meets any of the following criteria will be excluded from participation in this study:

1. Age less than 18 years
2. Greater than 168 hours since ARDS or pneumonia with mechanical ventilation onset
3. Pregnant or breastfeeding
4. Prisoner

5. Patient, surrogate, or physician not committed to full support (exception: a patient will not be excluded if he/she would receive all supportive care except for attempts at resuscitation from cardiac arrest)
6. No consent/inability to obtain consent or appropriate legal representative not available
7. Physician refusal to allow enrollment in the trial
8. Moribund patient not expected to survive 24 hours
9. No arterial line or central line/no intent to place an arterial or central line
10. No intent/unwillingness to follow lung protective ventilation strategy for subjects with ARDS
11. Severe hypoxemia defined as $\text{SpO}_2 < 95$ or $\text{PaO}_2 < 90$ on $\text{FiO}_2 \geq 0.9$
12. Hemoglobin < 7.0 g/dL
13. Subjects who are Jehovah's Witnesses or are otherwise unable or unwilling to receive blood transfusions during hospitalization
14. Acute myocardial infarction (MI) or acute coronary syndrome (ACS) within the last 90 days
15. Coronary artery bypass graft (CABG) surgery within 30 days
16. Angina pectoris or use of nitrates with activities of daily living
17. Severe cardiopulmonary disease classified as New York Heart Association (NYHA) class IV
18. Stroke (ischemic or hemorrhagic) within the prior 1 month, cardiac arrest requiring CPR within the prior 72 hours, or inability to assess mental status following cardiac arrest
19. Burns > 40% total body surface area
20. Severe airway inhalational injury
21. Use of high frequency oscillatory ventilation
22. Use of extracorporeal membrane oxygenation (ECMO)
23. Use of inhaled pulmonary vasodilator therapy (eg. nitric oxide [NO] or prostaglandins)
24. Diffuse alveolar hemorrhage from vasculitis
25. Concurrent participation in other investigational drug study

Reasons for Exclusions:

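### Section 7.2 lets an investigator who may know the allocation withdraw a dosed participant from the whole study for an adverse event, progression or a newly met exclusion criterion, and nothing requires follow-up afterwards

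*Combined protocol and SAP*

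**What the plan says.** Section 7.2 opens its list with "An investigator may discontinue or withdraw a participant from the study for the following reasons". Three grounds matter here:

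- an adverse event, laboratory abnormality or other condition that makes continued participation contrary to the participant's best interest;
- worsening illness, worded as "Disease progression which requires discontinuation of the study intervention";
- an entry bar that comes to light or arises after enrollment, worded as "If the participant meets an exclusion criterion (either newly developed or not previously recognized) that precludes further study participation".

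A fourth ground, never receiving a dose, is not at issue. The closing paragraph of 7.2 says that dosed participants who are later withdrawn are not replaced, so the section does reach dosed participants. Section 1.4 defines study withdrawal as permanent and as coming before study activities are complete.

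Other sections point the other way. Section 7.1: "Discontinuation from study drug does not mean discontinuation from the study, and remaining study procedures should be completed as indicated in the study protocol". Section 6.1.8: "Subjects who have their study drug permanently discontinued will continue their participation in the study". Section 6.1.6, for several conditions that are also exclusion criteria: "if a subject develops the following criteria during the study, the study drug will be held until resolved".

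On blinding, Section 6.3 says: "While the administering investigator will be unblinded throughout the study due to safety monitoring". That knowledge is limited to the investigator's own site. Section 7.2 does not reserve the withdrawal decision for a blinded physician.

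**The concern.** Safety is a primary endpoint, in 36 participants (24 iCO, 12 placebo). If an adverse event or worsening disease can end study participation, and not only dosing, later data go missing for reasons tied to outcome. Because the person deciding may know the arm, the loss could also depend on treatment. Sections 1.4 and 7.2 provide for seeking permission to keep collecting data only when the patient or surrogate asks to withdraw. They are silent when the investigator initiates the withdrawal. Two sites could treat the same patient in opposite ways, and each could cite the protocol.

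**Working it through.** **1. The passages side by side**

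| Situation after dosing | Section 7.2 | Elsewhere |
|---|---|---|
| Pre-specified administration-related event | May leave the study, on a best-interest judgement | 6.1.8: study drug permanently stopped, participation continues |
| Progression that requires stopping the intervention | May leave the study | 7.1: stopping drug is not leaving the study |
| New severe hypoxaemia, hemoglobin below 7.0 g/dL, ECMO, inhaled vasodilator (exclusions 11, 12, 22, 23) | May leave the study, if the criterion rules out further participation (undefined) | 6.1.6: drug held, with daily reassessment |
| New MI/ACS (exclusion 14) or stroke (exclusion 18) | Same | 6.1.6 applies new MI/ACS to further drug administration; 6.1.8 stops drug after MI or stroke within 48 hours and keeps the participant in |

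Section 7.2 is not made subject to 6.1.6, 6.1.8 or 7.1.

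**2. Does another section supply the missing follow-up?**

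- Section 9.3 keeps all dosed participants in the safety analyses. This preserves events already recorded but does not require later ones to be collected.
- Section 7.3 plans a National Death Index search for participants lost to follow-up or noted to have died. It defines loss as vital status that cannot be verified after discharge. That does not clearly describe someone withdrawn in the ICU.
- Section 9.4.3 names premature withdrawal as a source of bias, but its methods address missing data among survivors and long-term outcomes. Sections 9.4.2 and 9.4.5 make no such provision for safety.
- Section 8.7.7 has deaths during the study hospitalization reported to the DSMB. Deaths after discharge and non-fatal outcomes are outside it.

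**3. Which primary safety components match an exclusion criterion?** There are six. MI matches exclusion 14 ("Acute myocardial infarction (MI) or acute coronary syndrome (ACS) within the last 90 days") and stroke matches exclusion 18. Arrhythmia requiring cardioversion, COHb of at least 10% and the lactate rise have no counterpart. Worsening hypoxaemia is defined in 8.7.3 as a rise in FiO2 of at least 0.2 and in PEEP of at least 5 within 6 hours. Exclusion 11 is SpO2 below 95 or PaO2 below 90 on FiO2 of at least 0.9. A move from FiO2 0.4 and PEEP 5 to FiO2 0.6 and PEEP 10 meets the component without meeting the exclusion. So two of six match closely.

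**4. What could be lost.** Take a withdrawal on Day 2 as an example. Adverse-event collection could miss Days 3 to 7, which is 7 − 2 = 5 days. SOFA could miss Days 3, 4, 5, 7, 14 and 28, which is six of eight scheduled scores. Free-days to Days 28 and 60, vital status to month 6 and both neurocognitive tests could also be missed.

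**5. Scale.** The plan gives no figure for this point. The nearest is Table 6, the probability of at least one AE, 1 − (1 − p)^n. For the CO arm at p = 0.10 it states 0.90. With n = 24 the formula gives 0.920. With the 8% dropout stated in 9.2, 24 × 0.92 = 22.08, and n = 22 gives 0.902, which matches.

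That calculation treats loss as random and shrinks n. Under 9.3 a withdrawn participant stays in the denominator, so the better illustration keeps n = 24 and assumes that a share w of later events goes unseen: 1 − (1 − 0.10 × (1 − w))^24.

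| w (assumed) | P(at least one event seen) |
|---|---|
| 0 | 0.920 |
| 10% | 0.896 |
| 25% | 0.846 |
| 50% | 0.708 |

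Mortality, with two iCO participants withdrawn before death and dropped from the denominator (numbers of deaths assumed):

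| True deaths of 24 | True | Observed |
|---|---|---|
| 6 | 25.0% | 4/22 = 18.2% |
| 8 | 33.3% | 6/22 = 27.3% |
| 10 | 41.7% | 8/22 = 36.4% |

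The gap is about 5 to 7 points. If the two are instead censored in the planned Kaplan-Meier analysis, the middle row lies between 6/24 = 25.0% and 6/22 = 27.3%, depending on timing.

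Direction: suppose placebo has 4 deaths of 12 and one of the four is withdrawn, the same share as in iCO. It then shows 3/11 = 27.3%, and the between-arm difference stays at zero. With no placebo withdrawal it shows 4/12 = 33.3%, and iCO appears 6.1 points better by artefact.

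**The case against.** The strongest reply is that 7.2 is a residual clause. It is permissive, and its grounds are conditional: best interest for adverse events, and the undefined limit on participation for exclusion criteria. The specific rules in 6.1.6 and 6.1.8 act on study drug and could be taken to govern. Blinded coordinators collect adverse events and a blinded physician reviews them. Administration-related events are confined to 6 or 48 hours after a dose or to scheduled COHb samples ending at 180 minutes. A withdrawn patient receives no further dose, so only the tail of the last window is exposed.

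Much of this stands, and it limits the point. A reader might infer that patients with safety events drop out of the primary safety endpoint. The documents do not support that: Section 7.1 has new clinically relevant findings reported as adverse events, and 9.3 keeps every dosed participant in the safety set. A reader might also infer that the rule makes iCO look safer. That would need arm-dependent withdrawal, which the text permits but does not show.

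What does not stand is that the sections can be left to interpret one another. Nothing gives 6.1.6, 6.1.8 or 7.1 precedence over 7.2, and blinded review of adverse events cannot recover events that are no longer collected.

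**Conclusion.** The point holds as an unreconciled conflict with a missing follow-up rule, of moderate severity. Section 7.2 permits permanent withdrawal from the study on outcome-related grounds, by someone who may know the allocation, where other sections keep the participant in. The exposure is to later adverse events up to Day 7, SOFA, free-days, vital status and neurocognitive outcomes. It does not extend to the event that triggers withdrawal, and only MI and stroke among the six primary components closely match exclusion criteria.

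The size and direction of any bias are unknown. The detection probabilities and the 5-to-7-point mortality gaps rest on assumed event rates, deaths and withdrawals, none of which the documents give. The conflict in the text depends on none of those numbers.

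**What to change.** Reconcile 7.2 with 6.1.6, 6.1.8 and 7.1, so that an adverse event, progression or a newly met exclusion criterion acts on study drug, or on a burdensome study procedure, and does not by itself end follow-up. This leaves the question of which drug action applies to which event where it is.

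Keep the investigator's best-interest discretion over drug and procedures. It protects participants, and deleting it would go too far.

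Then state that, for every dosed participant, the following continue unless the patient or surrogate withdraws consent for data collection:

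- adverse-event collection to Day 7;
- vital status, with the National Death Index search in 7.3 extended explicitly to withdrawn participants;
- scheduled outcomes that are not burdensome.

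The cost is minor: a protocol wording change, and follow-up that is already on the schedule.
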